10.0 CRITERIA FOR EVALUATION AND ENDPOINT ANALYSIS

10.1 Response Criteria

Multiple Myeloma:

For the purpose of establishing one set of criteria for both Phase II and Phase III multiple myeloma studies, the following definitions will be used. These definitions are based on the International Uniform Response Criteria for Multiple Myeloma.

a. **Measurable Disease:** Measurable, quantifiable protein criteria must be present. Acceptable protein criteria are:

- Serum M protein ≥ 1 g/dL (≥ 10 g/L), quantified by using densitometry on serum protein electrophoresis (SPEP).

AND / OR

- Urine M protein [Bence-Jones Protein] ≥ 200 mg/24 hrs (≥ 0.2 g/24 hrs), quantified by 24-hour urine protein electrophoresis (UPEP, see Section [10.2.b](#)).

AND / OR

- Bone marrow plasma cells $\geq 30\%$

OR

- Patients who have both serum M protein levels < 1 g/dL AND urine M protein levels < 200 mg/24 hrs at baseline may be followed by serum free light chain (FLC) assay if involved free light chain level ≥ 10 mg/dL (≥ 100 mg/L).

Oligosecretory and Non-secretory Disease: Patients that do not meet the criteria for measurable disease above will be ineligible for this study.

b. **Objective Status:**

Stringent Complete Response (sCR):

- Meets all of the criteria for Complete Response (CR) and
- normal serum free light chain ratio and
- absence of clonal cells in bone marrow by immunohistochemistry or immunofluorescence

Complete Response (CR):

- Disappearance of all evidence of serum and urine M proteins on immunofixation electrophoresis studies **and**
- $< 5\%$ plasma cells in bone marrow **and**
- disappearance of any soft tissue plasmacytomas

Very Good Partial Response (VGPR):

- Meets all of the criteria for Partial Response (PR) **and**
- Serum and urine M proteins detectable by immunofixation but not on electrophoresis **or**
- $\geq 90\%$ reduction in serum M protein and urine M protein < 100 mg/24 hrs.

Partial Response (PR):

- If the patient had soft tissue plasmacytomas present at baseline and they were assessed at this disease assessment: $\geq 50\%$ reduction in size of soft tissue plasmacytomas (see Section [10.2.h](#)) **and**
- If the patient had $\geq 30\%$ plasma cells in bone marrow at baseline and a bone marrow biopsy was done: $\geq 50\%$ reduction in plasma cells **and**
- $\geq 50\%$ reduction in serum M protein and reduction in urine M protein $\geq 90\%$ or to $< 200 \text{ mg/24hr}$ **or**
- If patient had serum M protein $< 1 \text{ g/dL}$, urine M protein $< 200 \text{ mg/24 hrs}$, and an involved serum free light chain level $\geq 10 \text{ mg/dL}$ at baseline: $\geq 50\%$ decrease in the difference between involved and unininvolved serum free light chain levels

Stable Disease (STA):

- Patient does not meet criteria for Stringent Complete Response, Complete Response, Very Good Partial Response, Partial Response, or Progression.

Progression (PROG): Any one or more of the following:

- Serum M protein increase $\geq 25\%$ from lowest response level (or an increase of $\geq 1 \text{ g/dL}$ if serum M protein was $\geq 5 \text{ g/dL}$ at baseline), with an absolute increase of $\geq 0.5 \text{ g/dL}$ or
- Urine M protein increase $\geq 25\%$ from baseline (or lowest response level), with an absolute increase of $\geq 200 \text{ mg/24 hrs}$ or
- If patient had serum M protein $< 1 \text{ g/dL}$, urine M protein $< 200 \text{ g/24 hrs}$, and an involved serum free light chain level $\geq 10 \text{ g/dL}$ at baseline: $\geq 25\%$ increase in the difference between involved and unininvolved serum free light chain level, with an absolute increase of $\geq 10 \text{ mg/dL}$ or
- Bone marrow plasma cell percentage increase $\geq 25\%$ from baseline (or lowest response level), with the absolute plasma cell % $\geq 10\%$ or
- New bone lesions or soft tissue plasmacytomas, or definite increase in size of existing bone lesions or soft tissue plasmacytomas (see Section [10.2.h](#)) or
- Development of hypercalcemia (corrected serum calcium $> 11.5 \text{ mg/dL}$ or 2.65 mmol/L) that can be attributed solely to multiple myeloma

NOTE: If a disease assessment indicates that a patient is experiencing a Stringent Complete Response, Complete Response, Very Good Partial Response, Partial Response, or Progression, this should be confirmed by a second disease assessment (see Section [10.3](#)). The second disease assessment may be done at any time.

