10.2 Notes

- a. "M protein" may also be known by the following synonyms: M-spike, monoclonal protein, myeloma protein, monoclonal paraprotein, M-component.
- b. Urine M protein measurement is estimated using 24-hour urine protein electrophoresis (UPEP) only. Random or 24 hour urine tests measuring kappa and lambda light chain levels are not reliable and are not recommended.

- c. Patients with 'measurable disease' in both the serum and urine (serum M protein $\geq 1\text{ g/dL}$ and urine M protein $\geq 200\text{ mg/24h}$) at baseline need to be followed by both SPEP and UPEP for response assessment.
- d. Both serum protein electrophoresis (SPEP) and urine protein electrophoresis (UPEP) must be conducted at timepoints indicated in [Section 9.0](#). Patients with serum M protein $\geq 1\text{ g/dL}$ and/or urine M protein $\geq 200\text{ mg/24h}$ at baseline will be assessed for response based on SPEP and/or UPEP results only. Except for assessment of Stringent Complete Response, serum free light chain (FLC) assay response requirements are only applicable to patients who had serum M protein $< 1\text{ g/dL}$, urine M protein $< 200\text{ mg/24 hrs}$, and an involved serum free light chain level $\geq 10\text{ mg/dL}$ at baseline. A normal serum free light chain ratio is required for all patients for a Stringent Complete Response.
- e. To qualify for a Complete Response, both serum and urine immunofixation must be carried out and must be negative, regardless of the size of the baseline M protein in the serum or urine.
- f. Skeletal survey is not required for assessment of response unless clinically indicated, but is recommended once a year in clinical practice. Stringent Complete Response, Complete Response, Very Good Partial Response, Partial Response, and Stable Disease all require no known evidence of progressive or new bone lesions if radiographic studies were performed, but radiographic studies are not required to satisfy these response requirements.
- g. The size of the soft tissue plasmacytomas is defined as the sum of the products of the cross-diameters of each plasmacytoma. The size of the bone lesions will be determined in a similar manner. A definite increase in the size is defined as a $\geq 50\%$ increase (and at least 1 cm^2) of this sum.

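### For patients followed by free light chains, VGPR sets no light-chain threshold beyond PR's 50% fall and CR sets none, so depth of response is misgraded in both directions and some responses need no light-chain fall

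*Combined protocol and SAP*

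**What the plan says.** Section 10.1a lists the ways a patient can have measurable disease. The last is for patients below both M-protein thresholds (serum 1 g/dL, urine 200 mg/24 hrs), who "may be followed by serum free light chain (FLC) assay if involved free light chain level" is at least 10 mg/dL. A small spike, or none, is compatible with this route. Section 10.1b then grades response:

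- **PR** has two protein alternatives joined by 'or'. One is a 50% serum M-protein fall, with urine M protein down 90% or below 200 mg/24 hrs. The other, for the FLC group, is a 50% "decrease in the difference between involved and unininvolved serum free light chain levels".
- **VGPR** requires every PR criterion. It adds either "Serum and urine M proteins detectable by immunofixation but not on electrophoresis" or a 90% "reduction in serum M protein and urine M protein" below 100 mg/24 hrs.
- **CR** requires "Disappearance of all evidence of serum and urine M proteins on immunofixation electrophoresis studies", under 5% marrow plasma cells and no remaining plasmacytoma. It does not refer back to PR.
- **sCR** adds a normal FLC ratio.

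Note 10.2d says: "Except for assessment of Stringent Complete Response, serum free light chain (FLC) assay response requirements are only applicable to patients" in the FLC group. It tells the assessor to judge patients measurable by SPEP or UPEP on those tests only. It gives no matching instruction for the FLC group. Note 10.2e requires negative immunofixation for CR whatever the baseline M protein, and does not mention FLC.

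**The concern.** For a patient who qualifies through FLC, the light chain is the measurable disease. Between PR and sCR, however, the grading rests on M-protein tests that were below the measurable threshold at entry. A patient with M protein visible only on immunofixation meets the first VGPR condition before treatment starts. A patient with negative immunofixation may meet the CR protein condition with no change in light chains.

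Three planned uses are exposed. Section 11.5 compares the rate of PR or better between arms and also reports it for Arm 3. Section 11.6 uses biochemical CR as the explanatory variable for CR by PET. Sections 7.5g, 11.6 and 15.1 time the second PET by VGPR in patients with extramedullary disease.

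**Working it through.** The plan gives no figure on this point, so there is none to reproduce. The check applies 10.1b literally to an FLC-followed patient.

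**Inputs.** Baseline serum spike 0 or 0.6 g/dL (both below 1), urine M protein 0, no plasmacytoma, and baseline marrow below 30% plasma cells, so that PR's marrow condition does not apply. Current marrow is not done, 20% or 4%. The FLC difference falls by 0, 50 or 90%. M protein is taken as visible on immunofixation if either serum or urine is positive.

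**Step 1. PR judged on its FLC alternative only.**

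| Spike, baseline to current (g/dL) | Immunofixation | Marrow | FLC fall 0% | 50% | 90% |
|---|---|---|---|---|---|
| 0 to 0 | positive | any | stable | VGPR | VGPR |
| 0 to 0 | negative | not done or 20% | stable | PR | PR |
| 0 to 0 | negative | 4% | CR | CR | CR |
| 0.6 to 0.6 | positive | any | stable | PR | PR |
| 0.6 to 0.3 | positive | any | stable | PR | PR |
| 0.6 to 0.06 | positive | any | stable | VGPR | VGPR |
| 0.6 to 0 | positive | any | stable | VGPR | VGPR |
| 0.6 to 0 | negative | not done or 20% | stable | VGPR | VGPR |
| 0.6 to 0 | negative | 4% | CR | CR | CR |

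In the first row PR and VGPR cannot be told apart. In the fourth and fifth rows a 90% FLC fall earns only PR. In the two rows with negative immunofixation and 4% marrow, CR is reached at 0% fall. A light-chain rise large enough to meet the FLC progression criterion would be graded progression instead.

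**Step 2. PR's M-protein alternative.** Nothing in 10.1b or 10.2d closes it to FLC-followed patients. For 0.6 to 0.3 g/dL the serum fall is (0.6 − 0.3)/0.6 = 50%. The urine part (below 200 mg/24 hrs) is the entry condition itself. The 0%-fall cell in that row therefore becomes PR. For 0.6 to 0.06 the fall is (0.6 − 0.06)/0.6 = 90% with urine below 100, so that cell becomes VGPR with FLC unchanged. The same holds when the spike clears without qualifying as CR.

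**Step 3. What reaches an analysis.**

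- VGPR already requires PR, so the missing VGPR threshold adds 0 to the PR-or-better rate.
- CR without PR, and PR on the M-protein alternative, can each add responders. With an assumed 1, 3 or 6 such patients among 63 in an arm, the arm's rate rises by 1/63 = 1.6, 3/63 = 4.8 or 6/63 = 9.5 points. The between-arm difference moves only as far as these numbers differ between arms.
- If 5 to 15% of 126 patients are FLC-followed (an assumption), that is 126 × 0.05 ≈ 6 to 126 × 0.15 ≈ 19 patients. Section 11.6 expects extramedullary disease in 10 to 20%. If that holds in this group, the second PET is at issue in about 6 × 0.10 = 0.6 to 19 × 0.20 = 3.8 patients.

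**The case against.** The best reply is that the gap is narrow and the worst case remote.

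- **CR.** Disappearance presupposes something present at baseline. Section 4.1 normally requires monoclonal protein in serum or urine, and non-secretory disease is excluded. On-study marrow is done only as clinically indicated, and confirmed CR needs a marrow biopsy. All this makes the case uncommon. It does not close it: the last row of the table starts from a 0.6 g/dL spike that disappears, and is CR with FLC unchanged.
- **PR.** The FLC alternative opens with the baseline condition that defines the group, and 10.2d sorts patients by baseline type. Reading the alternatives as belonging to separate groups is natural and may be what was meant. But 10.2d restricts only the SPEP/UPEP group, so the text does not settle it.
- **Common criteria.** Section 10.1 aims at one set of criteria for Phase II and Phase III myeloma studies, and any local change departs from that. This is a fair cost.

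A reader might infer that VGPR has no FLC requirement at all. The documents do not support that: where PR is reached on FLC, VGPR inherits the 50% fall. Nor is every FLC-followed patient VGPR at 50%. That fails with a persisting spike, and with negative immunofixation and no baseline spike. It would also be wrong to say that depth is simply overstated, because the persisting-spike rows understate it.

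**Conclusion.** The point holds as a defect in a rule. For FLC-followed patients, 10.1b merges PR with VGPR in one pattern, withholds VGPR after a 90% FLC fall in another, and allows CR or PR without an FLC response in others. Notes 10.2d and 10.2e do not repair it.

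The reach is limited. The VGPR gap affects reported depth and, only in patients with extramedullary disease, the timing of the second PET. The CR and PR gaps can raise the secondary response rate, and the CR gap also enters the PET model, which the plan calls exploratory. A reader might infer that the primary comparison is compromised. It is not: PFS runs on the progression criteria, which have their own FLC rule, and not on the response category.

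The size cannot be fixed from the documents, because they do not state how many patients are FLC-followed or how many fall into each pattern. The 1.6 to 9.5 points rest on assumed counts. How often assay variation alone would halve a small spike also cannot be stated, because no assay error is given.

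**What to change.** Add to 10.1b, for patients with baseline serum M protein below 1 g/dL, urine M protein below 200 mg/24 hrs and involved FLC of at least 10 mg/dL only:

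- **PR:** judged on a fall of at least 50% in the involved-minus-uninvolved FLC difference. The serum/urine M-protein alternative does not apply. The plasmacytoma and marrow conditions stay.
- **VGPR:** a fall of at least 90% in that difference, in place of the two M-protein conditions. This mirrors the plan's own 90% serum rule.
- **CR:** the present conditions plus the FLC criterion for VGPR, so that the categories stay nested. A normal FLC ratio would be stricter, but the plan reserves it for sCR.

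With these clauses the first row of the table reads stable, PR, VGPR. The fourth row reads the same, so a 90% fall is no longer held at PR. The rows with negative immunofixation and 4% marrow read stable, PR, CR. A halved spike with unchanged FLC is stable.

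No new data are needed: Section 9.0 already schedules FLC at baseline and each cycle from Cycle 2. The cost is three clauses, a few patients changing category when response is scored, and a slight departure from the common criteria in 10.1.

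### The baseline qualifiers of the free-light-chain progression criterion are printed in grams, contradicting the milligram thresholds used elsewhere, so read literally some PFS progressions would be missed or dated late

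*Combined protocol and SAP*

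**What the plan says.** Section 10.1b lists six routes to progression and requires "Any one or more of the following". The third route is the only one based on FLC. It is restricted to patients with low serum M protein, urine M protein below 200 g/24 hrs, "and an involved serum free light chain level $\geq 10 \text{ g/dL}$ at baseline". For them it asks for at least a 25% "increase in the difference between involved and unininvolved serum free light chain level". Its rise threshold, by contrast, is in milligrams: "serum free light chain level, with an absolute increase of $\geq 10 \text{ mg/dL}$ or".

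The same patients are described in three other places, each time in milligrams:

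- **Section 10.1a, measurable disease.** Patients below the serum and urine limits "may be followed by serum free light chain (FLC) assay if involved free light chain level" is at least 10 mg/dL, with the equivalent 100 mg/L also printed.
- **Section 10.1b, Partial Response.** Urine M protein below 200 mg/24 hrs "and an involved serum free light chain level $\geq 10 \text{ mg/dL}$ at baseline".
- **Section 10.2, note d.** Apart from stringent complete response, "serum free light chain (FLC) assay response requirements are only applicable to patients who had serum M protein" below 1 g/dL, urine M protein below 200 mg/24 hrs and involved FLC of at least 10 mg/dL at baseline.

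Section 10.5 defines PFS by progression, symptomatic deterioration or death from any cause, and censors patients alive and progression-free at last contact. Section 1.1 makes PFS the primary objective.

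**The concern.** The threshold sits inside the primary endpoint. Patients measurable only by FLC are eligible under 10.1a, and FLC is the marker that section names for following them. With the printed units they can be scored as partial responders by FLC but not as progressing by FLC. Stable Disease in 10.1b is defined by exclusion. A patient with rising FLC and nothing else would therefore be recorded as stable and, if nothing further happened, censored at last contact.

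The other routes are looked at less often. FLC is scheduled every cycle (Study Calendar, footnote 11). After baseline, marrow is done as clinically indicated or at progression (footnote 4), and note 10.2f does not require a skeletal survey for response assessment unless clinically indicated. Progression that shows first in FLC could therefore be recorded late.

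The same definition feeds the Arm 1 crossover and the Arm 2 discontinuation provisions in Sections 5.2, 7.1 and 7.6, so a literal reading would reach beyond the analysis.

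**Working it through.** **1. The limits side by side**

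| Place | Urine M protein | Involved FLC at baseline |
|---|---|---|
| 10.1a Measurable disease | < 200 mg/24 hrs | ≥ 10 mg/dL (≥ 100 mg/L) |
| 10.1b Partial Response | < 200 mg/24 hrs | ≥ 10 mg/dL |
| 10.1b Progression | < 200 g/24 hrs | ≥ 10 g/dL |
| 10.2d | < 200 mg/24 hrs | ≥ 10 mg/dL |

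**2. Conversion**

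- FLC: 10 g/dL = 10 × 1,000 = 10,000 mg/dL = 100,000 mg/L. Ratio to the limit used elsewhere: 10,000 / 10 = 1,000.
- Urine: 200 g = 200,000 mg. Ratio: 200,000 / 200 = 1,000.

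The two errors act in opposite directions. The urine limit becomes so loose that it excludes practically no one. The FLC limit becomes so high that it admits practically no one, and it is hard to reconcile with the bullet's own requirement of serum M protein below 1 g/dL. Only the FLC limit blocks the route.

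**3. The plan's own design figures (11.2, 11.3)**

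Inputs: 63 patients per arm, medians of 9 and 15 months, one-sided alpha 0.1, power 90%, accrual A = 21 months, follow-up F = 18 months.

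- Schoenfeld events: d = 4(z_alpha + z_beta)² / (ln HR)² = 4(1.2816 + 1.2816)² / (ln 1.67)² ≈ 100. With HR = 15/9 it is 101.
- Event probability per arm: 1 − [exp(−λF) − exp(−λ(A+F))] / (λA), with λ = ln 2 / median. Expected events are 55.2 in Arm 1 and 45.4 in Arm 2, together 100.6.
- Power: Φ(√d × ln HR / 2 − 1.2816). At d = 100.6 and HR = 15/9 this is 0.900.

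The stated 100 events and 90% power are reproduced.

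**4. Illustrative loss**

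The share f of patients measurable only by FLC is not in the documents. I assume 5-20% (6.3 to 25.2 of 126 patients) and let m be the fraction of their events that is never recorded. Remaining events = 100.6 × (1 − f × m).

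| f | m = 0.5: events, power | m = 1: events, power |
|---|---|---|
| 5% | 98.1, 0.894 | 95.6, 0.888 |
| 10% | 95.6, 0.888 | 90.6, 0.875 |
| 20% | 90.6, 0.875 | 80.5, 0.844 |

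Section 11.3 waits for 100 progressions, up to 2 years of follow-up of the last patient. At that cap 107.8 events are expected. Half missed leaves 105.1 to 97.0 (power 0.909 to 0.891), and all missed leaves 102.4 to 86.2 (power 0.904 to 0.862), again for f = 5% and 20%.

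These figures use the unstratified approximation, spread the loss evenly over the arms, and count late-dated events as either present or lost. They indicate scale only.

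**The case against.** The intended units are easy to infer. Three other places give milligrams, 10.1a gives the FLC limit in two equivalent forms, and the faulty bullet states its own rise in mg/dL. A programmer or adjudicator would probably not apply the gram values, and nothing in the documents shows that anyone did. The bullet is the same for both arms, so no direction of bias in the hazard ratio follows from it. Since the error is a missing letter in text read by a program, the source PDF should be checked, although two gram units in one bullet with correct units around them make a reading slip less likely.

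Most of this stands, and it limits the consequence. It does not remove the contradiction: a threshold in the primary endpoint should not have to be inferred.

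A reader might also draw three stronger conclusions that the documents do not support:

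- **That these patients' progressions drop out of PFS.** One route of six is closed. The other five (serum M protein, urine M protein, marrow, bone lesions or plasmacytomas, hypercalcemia) carry no FLC qualifier, and symptomatic deterioration and death also count.
- **That every light-chain patient is affected.** Those with urine M protein of at least 200 mg/24 hrs are assessed by urine electrophoresis under 10.2d and keep the urine criterion. The bullet matters for patients measurable only by FLC.
- **That every event in the FLC-only group hangs on this bullet.** That treats all their events as visible only by FLC. It is the m = 1 column above, and it is not realistic.

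**Conclusion.** The contradiction is real. As printed, two baseline qualifiers in one bullet of 10.1b are 1,000 times those in 10.1a, the Partial Response bullet and 10.2d. Taken literally, the FLC route to progression is closed to the patients it was written for. It is most likely a misprint, but it sits in the definition of the primary endpoint and should be corrected.

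The supported consequence is that some progressions in FLC-only patients would be missed or dated late. The effect on power is modest: about 0.5 to 2.5 percentage points if half of those patients' events were missed, and up to about 5.6 points at the unrealistic bound. Both rest on an assumed 5-20% share and would be partly offset by the longer follow-up that 11.3 allows. The main harm is an endpoint definition that contradicts itself, rather than a design that fails.

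The permanent closure to accrual announced in the June 2016 memorandum does not make the point moot. Follow-up runs to 3 years after randomization (7.8), and progression still has to be adjudicated and programmed.

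**What to change.** In the third Progression bullet of 10.1b, change the urine limit to 200 mg/24 hrs and the involved FLC limit to 10 mg/dL, so that it agrees with 10.1a, the Partial Response bullet and 10.2d. Leave the rise threshold as it is, since it is already in mg/dL. Check the source PDF first to confirm that the gram units are printed there.

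Use the corrected units in the PFS derivation and in adjudication. For patients measurable only by FLC, check that no FLC progression already recorded was left out or dated late because of the printed units.

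The cost is two unit changes, which could go out by memorandum as the sponsor did for the patient number in Section 11.8. The sample size, the 100-event target and the 90% power do not change.

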4.0 STAGING CRITERIA

4.1 Diagnostic Criteria

Multiple Myeloma – normally all three are required, except for circumstances outlined in notes a-c.

Monoclonal plasma cells in the bone marrow $\geq 10\%$ and/or presence of a biopsy-proven plasmacytoma.^a

Monoclonal protein present in the serum and/or urine^b

Myeloma-related organ dysfunction (1 or more from the CRAB list below)^c

- [C] Calcium elevation in the blood (serum calcium > 10.5 mg/L or upper limit of normal)
- [R] Renal insufficiency (serum creatinine > 2 mg/dl)
- [A] Anemia (hemoglobin < 10 g/dl or 2 g $<$ normal)
- [B] Lytic bone lesions or osteoporosis^a

^a If a solitary (biopsy-proven) plasmacytoma or osteoporosis alone (without fractures) are the sole defining criteria, then $\geq 30\%$ plasma cells are required in the bone marrow.

^b If no monoclonal protein is detected (non-secretory disease), then $\geq 30\%$ monoclonal bone marrow plasma cells and/or a biopsy-proven plasmacytoma required.

^c A variety of other types of end organ dysfunctions can occasionally occur and lead to a need for therapy. Such dysfunction is sufficient to support classification as myeloma if proven to be myeloma related.

Diagnostic criteria are based on International Myeloma Foundation guidelines (<http://myeloma.org/main.jsp?type=article&id=1045>).

NOTE: Patients with light chain myeloma are eligible; however, patients with non-secretory disease are not eligible for this study. There are no exceptions to this based on diagnostic criteria in footnote "b" above.

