Footnotes for Study Calendar:

- 1 To be performed on Day 1 (\pm 3 days) of each cycle. H&P should include CTCAE Grade assessment of neuropathy.
- 2 Labs and physical assessment on Cycle 1 Day 1 may be omitted if pre-study labs were performed within 4 days of Cycle 1 Day 1. Results of Day 1 labs are not required prior to starting treatment for each cycle. If lab results do show existence of adverse events, the treating physician should refer to [Section 8.0](#), and otherwise continue treatment at their discretion.
- 3 Pre-study (within 14 days prior to registration), during Weeks 1 and 3, then every cycle or more often if clinically indicated.
- 4 Pre-study (within 28 days prior to registration) then as clinically indicated. Aspirate/biopsy is required at progression with patient consent.
- 5 Including magnesium, phosphate, sodium, potassium, chloride, bicarbonate, glucose, BUN, creatinine, bilirubin, SGOT/SGPT, calcium, albumin, LDH.
- 6 To be performed at baseline (Day 1 of Cycle 1), after Cycles 3, 6, 9, and 12 and at completion of treatment for any reason (unless performed within previous 28 days). For patients who cross over, to be performed every 3 cycles based on previous date of measurement.
- 7 Tests required for patients known to be positive for HIV, HepB or HepC to determine viral load; optional for all others. Pre-study to be done within 28 days prior to registration, if required.
- 8 Pre-study to be done within 28 days of registration, and at the time of documented disease progression or as clinically indicated.
- 9 Pre-study (within 28 days prior to registration), then after completion of treatment on Cycles 3, 6, 9 and 12, and at completion of treatment for any reason (unless EKG or ECHO has been performed within previous 28 days). For patients who cross over, to be performed every 3 cycles based on date of previous measurement. Crossover patients do not need to repeat Cycle 1 Day 1 tests, as long as patient is starting Arm 3 treatment within 28 days of prior testing (at time of progression) and the previous test results did not show a significant change from baseline. See Section [15.3](#) for ECHO imaging information, and Appendix [18.2](#) for AG Mednet image submission instructions.
- 10 See Section [15.1](#) for PET imaging information, and Appendix [18.2](#) for AG Mednet image submission instructions.

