10.5 Progression-Free Survival

From date of registration to date of first documentation of progression or symptomatic deterioration (as defined below), after having received the full-assigned Arm-specific dose of carfilzomib (27 mg/m² or 56 mg/m²), or death due to any cause. Patients last known to be alive and progression-free are censored at date of last contact.

Symptomatic Deterioration: The global deterioration of health status requiring discontinuation of treatment without objective evidence of progression.

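### The hypercalcemia limit for progression is given as 11.5 mg/dL or 2.65 mmol/L; these are different values and nothing says which one governs

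*Combined protocol and SAP*

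**What the plan says.** Section 10.1b defines progression as a list of alternatives: "Progression (PROG): Any one or more of the following". The last item begins "Development of hypercalcemia (corrected serum calcium", sets the limit at more than 11.5 mg/dL, and continues after the word *or* with "2.65 mmol/L) that can be attributed solely to multiple myeloma". A single greater-than sign precedes the pair. The note below the list says of an assessment showing progression that "this should be confirmed by a second disease assessment", which may be done at any time.

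Section 10.5 makes progression a PFS event. The interval runs "From date of registration to date of first documentation of progression or symptomatic deterioration" once the full assigned dose has been received, or to death. PFS is the primary endpoint (Sections 1.1 and 11.3).

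Calcium is measured routinely. Footnote 5 of the Section 9.0 calendar puts "creatinine, bilirubin, SGOT/SGPT, calcium, albumin, LDH" in the metabolic panel, which is scheduled in every cycle, at progression and in follow-up.

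Nothing in the supplied text says which of the two values governs, or that they are meant to differ.

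**The concern.** A limit printed in two units should be one limit written twice. Here the two figures describe different calcium levels, so two people applying Section 10.1b to the same result can reach different answers without either misreading it.

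The criterion matters because one item on the list is enough for progression, and progression enters the primary endpoint. It also has consequences for treatment. On Arm 1 it is one of several conditions for crossover under Section 5.2. On Arm 2, progression after the start of Cycle 2 ends protocol treatment (Section 7.1d). An endpoint definition should give one answer for one patient whatever unit the laboratory reports in.

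**Working it through.** **Inputs.** From Section 10.1b: 11.5 mg/dL and 2.65 mmol/L. The molar mass of calcium, 40.078 g/mol, is a physical constant and not a figure from the documents; values from 40.0 to 40.08 were tried.

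**Step 1: are unit pairs in this section meant as equivalents?** The pairs in Section 10.1a convert exactly:
- 1 g/dL × 10 = 10 g/L
- 200 mg / 1000 = 0.2 g
- 10 mg/dL × 10 = 100 mg/L

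The section's practice is to print the same limit in two units.

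**Step 2: convert the calcium pair.** The formula is mmol/L = mg/dL × 10 / molar mass.
- 11.5 × 10 / 40.078 = 2.87 mmol/L, where the plan prints 2.65.
- 2.65 × 40.078 / 10 = 10.62 mg/dL, where the plan prints 11.5.
- The gap is 11.5 − 10.62 = 0.88 mg/dL, or 2.87 − 2.65 = 0.22 mmol/L. The first limit is about 8.3% above the second (2.869 / 2.65 = 1.083).

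The implied equality does not reproduce.

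**Step 3: could rounding or the constant explain it?**
- Figures that round to 2.65 mmol/L (2.645 to 2.655) are 10.60 to 10.64 mg/dL.
- Figures that round to 11.5 mg/dL (11.45 to 11.55) are 2.857 to 2.882 mmol/L. The ranges do not overlap.
- Over molar masses of 40.0 to 40.08, 11.5 mg/dL stays between 2.869 and 2.875 mmol/L. Equality would need 115 / 2.65 = 43.4 g/mol.

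**Step 4: what each reading does.** The table takes three corrected calcium values, each attributed solely to myeloma, with no other criterion met. The conversions are 105 / 40.078 = 2.62, 110 / 40.078 = 2.74 and 120 / 40.078 = 2.99.

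| Corrected calcium | Judged in mg/dL (> 11.5) | Judged in mmol/L (> 2.65) | Either limit suffices |
|---|---|---|---|
| 10.5 mg/dL (2.62 mmol/L) | no | no | no |
| 11.0 mg/dL (2.74 mmol/L) | no | yes | yes |
| 12.0 mg/dL (2.99 mmol/L) | yes | yes | yes |

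Judged in the laboratory's own unit, the middle row depends on that unit. Under the either-limit reading it does not, but the last column then equals the mmol/L column throughout and 11.5 mg/dL decides nothing.

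**Step 5: does another section settle it?** Section 4.1 has a calcium cut-off of 10.5, printed in mg/L, or the upper limit of normal. It is a diagnostic criterion and does not say which progression limit was meant.

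**Step 6: how many events?** This would need the number of progressions resting on calcium alone, the share of those between 10.62 and 11.5 mg/dL, and the mix of reporting units across sites. The documents give none of these.

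**Step 7: other units in the same list.** The free light chain bullet describes its baseline subgroup with urine M protein below 200 g/24 hrs and involved free light chain of at least 10 g/dL. Section 10.1a, the partial response criterion in Section 10.1b, and Section 10.2d describe that subgroup with 200 mg/24 hrs and 10 mg/dL. The printed figures are 1,000 times larger, and the absolute increase in the same bullet is in mg/dL.

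**The case against.** The strongest reply is that this hardly matters in practice. The criterion applies only to hypercalcemia attributed solely to myeloma, progression should be confirmed, and most patients whose calcium rises may meet another criterion as well. Above 11.5 mg/dL both limits agree; at or below 10.62 mg/dL neither is met. The documents do not say how many laboratories report in mmol/L. Randomization is balanced and both arms share the wording, so no directional bias is shown.

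Most of this stands as a limit on size. Confirmation, however, does not resolve the ambiguity, because the second assessment is judged against the same two numbers.

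A reader might infer more than the documents support in three ways:
- *That the laboratory's unit decides the outcome as a matter of fact.* This is one of two readings of *or*. Under the other, a result is converted and judged alike everywhere.
- *That any patient between the two limits progresses in one unit.* The attribution condition still applies, and so does the expectation of confirmation. The unit also changes nothing if another criterion has already been met.
- *That every progression declared on calcium alone turns on the unit, for example 1 to 5 events if 1–5% of the planned 100 rest on calcium.* That share has no source in the documents, and the count would include patients above 11.5 mg/dL, who progress under both limits.

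**Conclusion.** The point holds as an error in a decision threshold of the primary endpoint. The two printed values differ by 0.88 mg/dL (0.22 mmol/L), and no rounding or plausible constant reconciles them. Either the reporting unit decides for a patient between about 10.62 and 11.5 mg/dL, or one of the printed numbers is redundant; the text does not say which.

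The exposed group is narrow: corrected calcium in that band, attributed solely to myeloma, and no other progression criterion met. The number of PFS events involved cannot be computed and is probably small. The target of 100 events, the one-sided alpha of 0.1 and the 90% power in Sections 11.2 and 11.3 do not depend on it. The only outside input is the molar mass of calcium. Which threshold is clinically right is not judged here.

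**What to change.** In Section 10.1b the sponsor should reconcile the two values and print one intended limit with its correct conversion: 11.5 mg/dL goes with 2.87 mmol/L, and 2.65 mmol/L with 10.62 mg/dL. That single limit should be applied to all patients in the PFS derivation. In the same edit, the gram units in the free light chain bullet should be reconciled with the milligram units in Sections 10.1a and 10.2d.

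The text change is one number and two units. Accrual is closed, so the practical work is at analysis: list progressions that rest on calcium alone, check the recorded calcium, albumin and unit, and apply the stated limit. If any patient was declared progressed on the lower value and the sponsor intended the higher, later assessments may be missing, because footnote 13 of Section 9.0 no longer requires response assessments after progression. The derivation should say how such a patient is handled.
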